13.4.2 New diagnosis of myopathy

All participants will be advised to discuss a new diagnosis of myopathy with their usual treating GP. The decision to cease or reduce the study medication will be made by the GP in consultation with the participant. The participant will continue in the study on a reduced dose or remain off study medication and have routine follow up (study visits and phone calls) for observational purposes (see section 7.1).

13.4.3 Liver impairment

Liver impairment defined as:

- 1) an elevated ALT and/or AST across two or more tests (elevations greater than 3x ULN and elevated bilirubin (2x ULN)) and
- 2) no other demonstrable cause.

14. Adherence to Ethical, Regulatory and Administrative Considerations

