5.2.3 Exclusion criteria

Potential participants who meet any of the following criteria will be excluded from the study:

- A history of clinical cardiovascular disease (defined as myocardial infarction, angina, coronary artery angioplasty and/or stenting, coronary artery bypass grafting surgery, heart failure, stroke, transient ischaemic attack (TIA), carotid stenosis, abdominal aortic aneurysm and peripheral vascular disease),
- Clinical diagnosis of dementia, treatment with medications for dementia (e.g. donepezil (Aricept), rivastigmine (Exelon) or Galantamine (Galantyl) or a 3MS score < 78 on screening.
- A history of diabetes or evidence of diabetes on pathology results (WHO diagnostic criteria whereby HbA1c $\geq 6.5\%$ / 48 mmol/mol or fasting glucose ≥ 7.0 mmol/L on two consecutive tests),
- Total cholesterol > 7.5 mmol/L,⁴⁹
- Moderate or severe chronic kidney disease (persistent proteinuria whereby urine albumin: creatinine ratio > 30 mg/mmol⁵⁰ and/or eGFR < 45 ml/min/1.73m² on two consecutive tests),⁴⁹
- Moderate or severe liver disease (persistent elevations of transaminases of more than 3 times the upper limit of the normal laboratory reference range),
- Serious inter-current illness likely to cause death within the next 5 years such as terminal cancer or obstructive airways disease,
- Current participation in another interventional clinical trial,
- Absolute contraindication to statin therapy,
- Current use of statin therapy or other lipid lowering therapy for primary prevention and unwilling to stop therapy,

- Current long term or permanent use of potent cytochrome P450 (CYP) 3A4 inhibitors as specified in Appendix 3.

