5.6.1 Screening call

Potential participants will phone the study centre after they have received an invitation to participate in the study. At this phone screening call, they will be screened for eligibility to be included in the study. Those who pass this first screening stage will then be invited to attend baseline visit 1.

Figure 3: Participant Timeline

[figure not shown]

Table 2: STAREE measurement and study activity schedule. A single X (with no superscripts) indicates that all specified measures carried out. The presence of a superscript indicates that the corresponding specific assessment is performed at that time point.

Measurement/ Activity	Screening	Baseline visits (BV)			Post-randomisation			
	Screening call	BV 1	GP visit	BV 2	1 month call	Annual visits (without cognitive testing)	Annual visits (with cognitive testing)	Close out visit
Type of visit	phone	clinic or phone	clinic or telehealth	clinic or phone	phone	clinic or phone	clinic or phone	clinic or phone
Month in trial (week)	0	0	0	0	(4)			
Review inclusion/ Exclusion criteria	X	X	X	X				
Obtain informed consent		X						
Dispense study medication (supply posted after annual study visit once compliance checked)		X (run-in med only)		Posted (after randomisation)				
Medication titration					X			
Assess medication compliance				X		X	X	X
Concomitant medications		X				X	X	X
Blood pressure & heart rate/rhythm ^a , height ^b , weight ^c , waist:hip ratio ^c		X ^{a,b,c}				X ^{a,c}	X ^{a,c}	X
Lifestyle profile & personal medical history ^d , family medical history ^e & IPAQ-E ^f , physical function		X ^{d,e}		X		X ^{d,f}	X ^d	X ^d
Routine Laboratory testing, GP referral to local pathology Bloods ^{**} : fasting glucose ¹ , fasting lipids (TC, HDL, LDL, triglyceride) ¹ , Hb ² , CK ² , creatinine ³ , (eGFR) ³ , ALT ³ , AST ³ , HbA1c ³ , Urine: ACR ³		X ^{1,2,3}				X ³	X ³	X ^{1,3}
Measurement/ Activity	Screening call	BV 1	GP visit	BV 2	Post-randomisation			

	Screening	Baseline visits (BV)			Post-randomisation			
	Screening call	BV 1	GP visit	BV 2	1 month call	Annual visits (without cognitive testing)	Annual visits (with cognitive testing)	Close out visit
Type of visit	phone	clinic or phone	clinic	clinic or phone	phone	clinic or phone	clinic or phone	
Month in trial (week)	0	0	0	0	(4)			
Quality of life SF-36				X		X	X	X
Assess cognitive function 3MS [±] (and CES-D 10 to exclude depression); CAM ¹		X					X	X

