5.7.4 Annual Follow up visit

Each year after randomisation, participants will participate in a study visit with a Field Officer. Visits may be conducted face-to-face or by phone. Annual measurements will include cognitive tests and disability assessments, lifestyle questionnaires as well as physical measures. The Quality of Life (SF-36), Life Ability and Annual medical history questionnaires will be provided in an online format or posted to participants who have agreed to this. For all other participants these surveys will be conducted at face-to-face visits. Pathology will be repeated (excluding lipids). Participants will be asked about their recent medical history and any concomitant medications they are taking. Additionally, participants will be asked about serious adverse events (SAEs) and potential study endpoints.

Following notification, clinical information relating to any SAE or endpoint will be sourced through: a) medical record review and b) hospital records and discharge summaries.

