13.3 Safety reporting

In general, only AEs pre-specified to be of specific interest and those that are deemed to be serious will be reportable. AEs of interest are diabetes, myopathy (muscle symptoms) and liver impairment.

All SAEs will be reported from the study sites directly to the study medical officer within 24 hours of their notification to the clinical sites (study centres).

SAEs will be reviewed by the medical officer and adjudicated as related or unrelated to study medication, and as expected or unexpected serious adverse events.

All SAEs and SUSARS will be reported by the study centre to the ethics committees and DSMB according to the following schedule:

- Related and expected SAEs, will be reported to the Human Research and Ethics Committee (HREC)
- Related and unexpected SUSARs will be reported to the HREC within 72 hours and to the RACGP and TGA within 15 days and followed up with detailed reports when available
- Unrelated SAEs will be reported to the STAREE DSMB bi-annually

All SAEs and SUSARs will be reported to the DSMB in summary format by blinded treatment arm (A and B).

The data and safety monitoring reports will be prepared by an independent statistician.

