13.4 Adverse Events of Interest

13.4.1 New diagnosis of diabetes

Diabetes as diagnosed on the basis of:

1) an annual HbA1c or fasting plasma glucose test using the WHO criteria (a HbA1c value of 6.5% or higher or a fasting plasma glucose of 7.0 mmol/L or higher, with confirmation by a second test within 4 weeks; or

2) community-based testing during usual clinical care (GP or other clinicians e.g. hospitalisation with a hyperglycaemic crisis or classic symptoms of hyperglycaemia and a random plasma glucose test of 11.1 mmol/L and/or commencement of glucose lowering medication for glucose control).

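### Liver impairment, a pre-specified adverse event of interest, needs a bilirubin result that the scheduled laboratory tests do not include, so its ascertainment depends on discretionary testing

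*Protocol*

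**What the plan says.** Section 13.3 limits routine reporting largely to serious events and to a short list of others: "AEs of interest are diabetes, myopathy (muscle symptoms) and liver impairment".

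Section 13.4.3 sets two conditions for liver impairment, both required. The first is raised ALT and/or AST on two or more tests, qualified as "elevations greater than 3x ULN and elevated bilirubin (2x ULN"). The second is "no other demonstrable cause".

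Table 2 (section 5.6.1) gives the schedule in a row labelled "Routine Laboratory testing, GP referral to local pathology". It names each analyte and splits even the lipid panel into its parts: "fasting lipids (TC, HDL, LDL, triglyceride"). The full list is fasting glucose, lipids, Hb, CK, creatinine, eGFR, ALT, AST, HbA1c and urine ACR.

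For follow-up, section 5.7.4 says "Pathology will be repeated (excluding lipids"). It adds no analyte.

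The liver exclusion in section 5.2.3 also rests on transaminases only: "persistent elevations of transaminases of more than 3 times the upper limit of the normal laboratory reference range".

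**The concern.** A safety outcome that the protocol names in advance should be classifiable from data that the protocol arranges to collect. Here one required element, bilirubin, is outside the schedule. Two participants with identical repeated ALT values could be classified differently only because one doctor ordered bilirubin and another did not.

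This matters because section 5.3.2 presents the balance of benefit and harm in people over 70 as an open question for the trial, and section 2.4.5 says it is unknown whether statin-related liver damage is more frequent at older ages. A by-arm count of liver impairment would be read as evidence on that question. Without a record of who had bilirubin measured, a low count could mean few events or few tests, and the reader could not tell which.

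**Working it through.** The protocol states no figure for this event, so there is nothing to reproduce. The check compares what the definition needs with what each scheduled visit supplies.

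**Analytes needed (section 13.4.3):** ALT and/or AST, and bilirubin.

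**Analytes supplied (Table 2, using its group numbers):**

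| Visit | Groups tested | ALT, AST | Bilirubin |
|---|---|---|---|
| Baseline visit 1 | 1, 2, 3 | yes | no |
| Annual visits | 3 | yes | no |
| Close-out visit | 1, 3 | yes | no |

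Group 1 is fasting glucose and lipids. Group 2 is Hb and CK. Group 3 is creatinine, eGFR, ALT, AST, HbA1c and ACR. Section 5.7.4 describes the annual repeat a little more broadly than Table 2, since it removes only lipids, but bilirubin is absent on either reading.

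**Could another section supply bilirubin?**

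- In the text shown, bilirubin is mentioned only in the definition itself.
- No section requires a bilirubin test after a raised ALT or AST.
- Eligibility uses transaminases only, so there is no baseline bilirubin either.
- The diabetes definition in section 13.4.1 accepts a second source, "community-based testing during usual clinical care". The liver definition names no such source.

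**Result.** The transaminase part can be assessed at every scheduled laboratory visit and the bilirubin part at none. Because the two are joined by *and*, scheduled tests alone cannot place any participant in either arm in the category, however high the ALT or AST.

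The definition is also unclear on one detail: the bracketed wording does not say whether bilirubin must be raised on one test or, like the transaminases, on two or more.

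**The case against.** The strongest reply is that the definition was never meant to run on scheduled tests alone. Excluding other causes needs a clinical work-up that no annual panel provides. Section 8 sends any out-of-range result to the participant's GP, section 13.2 repeats this for abnormal tests, and treating GPs are co-investigators where possible. Section 13.2.2 allows supporting documents for adverse events, and section 5.7.4 has medical and hospital records collected for serious ones. Bilirubin can reach the trial by these routes. This stands: the event is not undetectable. What remains is that none of the routes requires the test, so ascertainment is not systematic.

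Appendix 6, cited in section 5.5 for laboratory detail, is not shown and might list bilirubin. That also stands as a limit on the finding. If it does, it disagrees with Table 2, and one of them needs correcting.

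A reader might go further in four ways that the protocol does not support.

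- *The count will be near zero whatever the drug does, because of the missing test.* Section 2.4.5 cites fewer than 2 serious statin-associated liver injuries per million patient-years. Section 12 plans 58,135 person-years. With equal arms (an assumption), 58,135 / 2 = 29,067.5, and 29,067.5 x 2 / 1,000,000 = 0.058, so fewer than about 0.06 statin-arm cases. That rate comes from spontaneous reports, may be too low, and matches the definition only roughly. Even so, a very low count would be expected with bilirubin at every visit.
- *The 0.5-2.0% with raised enzymes in section 2.4.5 gives the number of missed cases.* That figure concerns mild elevations, which the section calls usually transient. It does not say how many exceed 3x ULN or do so twice.
- *The annual transaminase results will go unreported.* Nothing says so. The analysis plan and the data monitoring board's charter and plan are not shown and may tabulate them. Hospitalised, life-threatening or fatal liver injury is reportable as a serious event regardless of bilirubin.
- *The exclusion criterion contradicts the event definition.* A screening rule and a drug-injury definition may use different thresholds.

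**Conclusion.** The mismatch is real and limited. A pre-specified, reportable adverse event of interest requires an analyte that appears at none of the scheduled laboratory visits, and the protocol as shown neither requires it on follow-up nor names an outside source for it. Classification therefore depends on discretionary testing by GPs or hospitals, and a missing bilirubin cannot be distinguished from a normal one.

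The number of misclassified participants cannot be estimated: the protocol gives neither the frequency of repeated values above 3x ULN nor the frequency of bilirubin testing in usual care. The point affects one safety outcome and no primary or secondary endpoint. It assumes that Table 2 is the complete schedule, which Appendix 6 could alter. It makes no claim about which clinical threshold is right.

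**What to change.** 1. Reconcile section 13.4.3 with Table 2, and with Appendix 6 if that lists bilirubin, so that the definition and the data collected match. State where the bilirubin result comes from and whether one raised value is enough. The choice of clinical criterion stays with the investigators.
2. Pre-specify a by-arm safety line for ALT and/or AST above 3x ULN on two or more tests, using the annual results already collected, and say which tests count towards the two.
3. Beside it, show separately the events that also meet the bilirubin criterion from clinical records, and give by arm how many participants with repeated transaminase elevation had bilirubin measured. That denominator separates a normal result from no result.

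The cost is a wording change and an extra safety table line with its breakdown. The by-arm line needs no new test or visit. The downside is that it will list milder events, so it should be labelled as laboratory elevations and not as liver impairment.

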14.1 Ethical considerations

14.1.1 General

This study will be conducted in accordance with the Declaration of Helsinki 1964 as revised in Edinburgh in 2000 and with the National Health & Medical Research Council (NHMRC) Guidelines on Human Experimentation.

14.1.2 Ethics Committee Approval

The primary ethics committee for the study is the Monash University Human Research Ethics Committee (Project ID 2787 and 21528).

The study has also been reviewed and approved by the following ethics committees:

Curtin University Human Research Ethics Committee (HR113/2015)

RACGP National Research and Evaluation Ethics Committee (14 - 017)

Tasmanian Health and Medical Research Ethics Committee (H0014918)

University of Newcastle Human Research Ethics Committee (H-2016-0266)

14.1.3 Information for participants

Before obtaining consent from the participant they must be informed of the objectives, benefits, risks and requirements of the study, as well as the nature of the study medication. A participant consent form will be provided to every participant prior to baseline visit 1 (posted if time permits) or at baseline visit 1.

14.1.4 Informed consent

- a) All participants must give their written informed consent at baseline visit 1 to continue in the study.
- b) Informed consent is obtained from the participant by the STAREE Field Officers. The study staff should fully inform the participant of all pertinent aspects of the STAREE study by reviewing the study information and consent form. All participants should be informed to the fullest extent possible about the study, in language and terms they are able to understand.
- c) Prior to a participant's involvement in the study, the written Informed Consent Form should be signed, name filled in and personally dated by the participant and by the staff member who conducted the informed consent discussion. A copy of the signed and dated written Informed Consent Form will be provided to the participant. The original consent form is to be stored in the participant's individual study file, held by the investigator.
- d) The form used for obtaining the participant's informed consent must be the current version that has been reviewed and approved by the appropriate Ethics Committee.

14.1.5 Protocol Amendments

All amendments and revisions to the trial protocol will be submitted to the Monash University Human Research Ethics Committee and on approval will be communicated to STAREE investigators and relevant staff through internal processes such as email and group meetings. All updates will be chronologically documented in the current version of the protocol.

14.1.6 Confidentiality

All study-related information will be stored securely at the study sites. All participant information will be stored in locked filing cabinets in areas accessible only by STAREE personnel. All participant CRFs will contain a coded identification number only to maintain participant confidentiality. All records that contain names or other personal identifiers, such as informed consent forms, will be stored separately from study records identified by code number. All local databases will be secured with password-protected access systems. Other forms and lists, that link participant ID numbers to other identifying information will be stored in a separate, locked file in an area with limited access. Hardcopy information will be uploaded into a secure study database housed in the high security Monash University Data Centre at Clayton, Melbourne. All information collected for this project will be retained for a period of no less than 15 years following the completion of the project. Hardcopy information will be shredded and destroyed, and electronic data will be deleted from the secure STAREE database after a period of no less than 15 years after the completion of the project, in accordance with the Monash University Human Research Ethics Committee recommendations for drug trials and Good Clinical Practice Guidelines.

14.2 Regulatory considerations

14.2.1 Financing

Monash University is the sponsor of the STAREE trial.

STAREE has been awarded project grants from the NHMRC (Australia) (APP1068146 and APP1161503) and from the Heart Foundation (#101663). STAREE MIND and STAREE HEART have been awarded NHMRC grant funding (#2006611 and #1165440).

14.2.2 Trial registration

STAREE is registered with clinicaltrials.gov (Identifier NCT02099123). First posted March 28, 2014.

14.2.3 Declaration of interest

The STAREE investigators have established a policy regarding Conflict of Interest. The policy aims to protect the integrity of the project's decision-making process and to manage risk. The policy requires full disclosure by all of the investigators of their, and their immediate families, financial relationships with all pharmaceutical and biomedical companies judged to have an active or potential interest in the conduct and outcome of the study. The disclosures of each project investigator will be documented in all publications.

14.3 Indemnity

Monash University shall at all times indemnify the study investigators and their staff from claims that may be made against them for any injury sustained by a study participant as a consequence of the follow up for this study as outlined in this protocol. GPs insurers will be asked to indemnify the GP co-investigators who are participating in the study. Ramsay Healthcare will indemnify the study medication.

14.4 Data Access

The Data Access and Publications Committee will oversee the intra-study data sharing process, with input from the STAREE Executive Committee.

Access to STAREE data for analysis, preparation and submission of publications and presentations will be decided according to the STAREE Data Access Policy and the STAREE Publications Policy.

The policies are based on the following principles:

- STAREE data is to be used for the purposes of furthering the public good in relation to health.
- STAREE data is a collaborative resource. Data elements cannot be reserved by researchers for exclusive use.
- STAREE data is to be used for projects that are scientifically, methodologically and ethically sound.
- The privacy of STAREE participants is to be protected.

14.6 Administrative Organisation

14.6.1 Individual and committee responsibilities

Principal Investigators: [name] and [name]

STAREE Executive Committee

The STAREE Executive Committee will be responsible for the overall design, management and conduct of STAREE including preparation of the protocol and revisions, preparation of investigators brochure and case report forms (CRFs), publication of study reports, approving the operational plan for the study, and financial management of the trial. The committee will monitor the progress of recruitment against targets, and if necessary, institute remedial actions. It will also review the rates of adherence to randomised treatments and the data from the quality assurance program.

National Operations Committee

The National Operations Committee will be responsible for implementing the study, monitoring the progress of recruitment and ensuring adherence and standardisation through the study. It will also need to ensure the coordination, consistency and transfer of data to the Data Management Centre. The committee will ensure quality control review of laboratory

data, clinical measurements and data collection, completeness and entry times of data, site monitoring and source documentation. These committees may consist of the Principal Investigator or Project Managers and other key research personnel who will report directly to the Steering Committee.

Internal Data Monitoring Committee (DMC)

The STAREE Internal Data Monitoring Committee (DMC) is responsible for reviewing information related to the conduct of the trial and monitoring activity as per STAREE's Monitoring Plan, Monash University's Research Data Management Guidelines and the NHMRC's Australian Code for the Responsible Conduct of Research. The STAREE Internal DMC shall make recommendations to the Monash University STAREE Executive Committee. Recommendations shall include all aspects of Data Monitoring as per the STAREE Monitoring Plan.

DMC members will be appointed by the Executive and Management of the STAREE Clinical Trial and may be involved in the study's collection and management of data, including data monitoring. Appointed committee members will include a Committee Chair, Data Statistician and an individual who has had previous experience with a DMC or experience with trials of medicinal investigational products.

Data Safety and Monitoring Board

The Data Safety and Monitoring Board (DSMB) will monitor the establishment and implementation of the STAREE Data Management System and review all safety, data and quality assurance reports for the study. The DSMB chair will report to the Steering Committee of STAREE on data management issues associated with the study and will provide recommendations to the Steering Committee in relation to subject recruitment, event rate tracking, monitoring adverse events and conducting interim analyses. The committee will operate in accordance with the DSMB Charter and Plan.

The DSMB will have responsibility for monitoring quality control of the data, progress of recruitment and safety aspects of the trial. The DMC will present data for review by the DSMB by a blinded treatment arm (e.g., 'A' and 'B'). The DSMB will monitor all-cause mortality rates in the two randomised groups. Additionally one pre-specified interim analysis may occur when an average of 3.25 years of follow up per participant has accrued and >50% of the primary endpoints have occurred. The DSMB will be responsible for reviewing any interim analysis on unblinded data and providing recommendations to the trial executive committee. The DSMB will review deaths, serious adverse events and other endpoint data on a periodic basis. Administrative support will be provided by an independent biostatistician and research assistant.

The DSMB will be provided with data every 6 months or as requested. The DSMB will meet annually for the first 2 years and thereafter will meet twice annually, by teleconference or in-person where possible to review study progress, data quality control, address policy issues and review total mortality data, adverse events and all safety data and monitor the study progress and data quality. The DSMB has expertise related to the conduct of clinical trials *per se* and in the primary care sector, the elderly, epidemiology, biostatistics, clinical pharmacology, clinicians, and cardiovascular disease. Confidentiality will be maintained

during all phases of the trial including monitoring, preparation of interim results, review, and response to monitoring recommendations.

Endpoint Adjudication Committees (EACs)

The Endpoint Adjudication Committees (EACs) will be responsible for developing adjudication criteria and processes to capture key data required for the identification and adjudication of the following study endpoints: All-cause mortality, myocardial infarction, heart failure, stroke, and dementia. The EACs will operate in accordance with the Endpoint Adjudication Committee Charter.

The following EACs will be responsible for the assessment of suspected endpoints through examination of relevant clinical information and for their adjudication according to the pre-specified endpoint definitions.

Death Subcommittee

Dementia Subcommittee

Heart Disease (Myocardial Infarction) Subcommittee

Heart Disease (Heart Failure) Subcommittee

Stroke Subcommittee

The EAC subcommittees will be chaired by specialist clinicians with expertise to oversee adjudication of the relevant endpoints. All EAC members will be selected by the STAREE Executive Committee and will be appointed for the duration of the study. Administrative support, training and source documentation required for EAC members to carry out their roles will be provided by the EAC Coordinator and STAREE study staff.

Data Access and Publications Committee

The Data Access and Publications Committee will be responsible for developing and implementing the data access, sub-studies and ancillary studies, and publication policies. It will oversee the processes of receiving, reviewing and approving applications from researchers for STAREE baseline data, for conduct of sub-studies and ancillary studies, and requests for publication, approval for abstracts and submission to conferences. Authorship of publications will be guided by the STAREE data access and publications policies.

General Practice Advisory Committee

The General Practice Advisory Committee will advise the National Operations Committee and other committees on aspects of the trial related to family practice.

Public Advisory Group

The STAREE Public Advisory Group will be a forum to facilitate the flow of information from the STAREE clinical trial to the public. It will also provide opportunities for members of the group to provide feedback and input from the community perspective on how information is disseminated to the public about the STAREE trial.

STAREE Healthy Ageing Biobank Steering committee

Access and utilisation of the biospecimens stored in the STAREE Healthy Ageing Biobank will be governed by the STAREE Healthy Ageing Biobank steering committee. The STAREE

Healthy Ageing Biobank steering committee will review detailed proposals outlining the research to be undertaken, and access to biospecimens will only be granted if the proposals are assessed to have scientific merit and are adequately funded. Accurate records of the aliquots of each stored biospecimen will be achieved through the use of a Nunc Next Generation CryoTube Scanner and software. The software will be utilised to track each sample which will include storage or retrieval of a specimen by an approved researcher. Any secondary research which uncovers significant genetic information will be notified to the Biobank Steering committee, which will determine who will be notified about these results.

STAREE MIND Steering committee

The STAREE MIND Steering Committee will oversee integration of STAREE MIND with the parent trial. It will be responsible for design, management and conduct of STAREE MIND including preparation of the protocol, investigators brochures and case report forms (CRFs), publication of study reports, approval of the operational plan, financial management and will monitor the progress of recruitment. The STAREE MIND committee will report on progress to the STAREE Steering and Executive committees.

STAREE HEART Steering committee

The STAREE HEART Steering Committee will oversee integration of STAREE HEART with the parent trial. It will be responsible for design, management and conduct of STAREE HEART including preparation of the protocol, investigators brochures and case report forms (CRFs), publication of study reports, approval of the operational plan, financial management and will monitor the progress of recruitment. The STAREE HEART committee will report on progress to the STAREE Steering and Executive committees.

14. Data Management and Training

